The primary outcome is OCD severity as assessed by the blind rater-administered Yale-Brown Obsessive-Compulsive Scale (Y-BOCS). Specifically, we will test whether B4DT is non-inferior to

standard CBT 14 weeks after treatment start. The non inferiority margin is set to 4 points on the Y-BOCS.

Non-inferiority designs test whether a novel treatment is not unacceptably less efficacious (in this case, 4 points) than another treatment whose efficacy has already been established. However, a non-inferiority study may also be used to test for superiority without inflating the false-positive rate [7]. We will therefore sequentially test 1) whether B4DT is non-inferior to gold standard CBT , and 2) whether B4DT is superior to gold standard CBT.

Secondary outcomes

Our secondary objectives are to compare B4DT and gold standard CBT with regards to:

- 1) Time to response. We hypothesize that B4DT, due to its intensive design, will provide a faster response than gold- standard CBT. A comparison of the proportion of treatment responders at week 4 and week 7 will be used to test this hypothesis.
- 2) Rates of response and remission. The proportion of participants in response and remission will be compared 14 weeks after treatment start. For these outcomes, we have no directed hypotheses.
- 3) Dropout rate. We will test whether the proportion of patients that discontinue treatment prematurely (i.e., complete less than 50% of the treatment) differs between the B4DT and the gold standard CBT arm. For this outcome, we have no directed hypothesis.
- 4) Cost-effectiveness. Health economic data will be collected using clinic data on therapist usage and the Treatment Inventory of Costs in Psychiatric Patients [11]. Between-group costs will be calculated and compared 14 weeks after treatment start. The emphasis will be on cost-effectiveness analyses using responder status as outcome and health-care provider as the cost perspective. For this outcome, we have no directed hypothesis.
- 5) Negative effects. The total score of the Negative Effects Questionnaire will be compared 14 weeks after treatment start, as well as the prevalence of severe adverse events. For this outcome, we do not have a directed hypothesis.

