The primary outcome measure is the blind assessor-rated Y-BOCS, which will be administered at pre-treatment, at weeks 4 and 7 during treatment, 14 weeks after treatment start (primary endpoint), and at the 7- and 16-month follow-ups [21]. Blinded assessors will undergo training prior to conducting clinician-rated assessment and practice on videos of OCD case examples. In order to be allowed to conduct assessments for the project, the assessors will have to deviate no more than 1 point on single items, no more than 2 points on the obsessions subscale and the compulsions subscale and no more than 4 points on the Y-BOCS total score compared to expert raters at the two clinics. Inter-rater reliability on the Y-BOCS will be reported.

Secondary clinician-administered outcome measures are the Clinical Global Impression – Severity and Improvement (CGI-S, CGI-I), the Patient Exposure/Response Prevention Adherence Scale (PEAS), the Structured Clinical Interview for DSM-5 for OCD and related disorders (SCID-5) and the Mini International Neuropsychiatric Interview. SCID-5 and MINI will be administered at pre-treatment to confirm the OCD-diagnosis and assess comorbidities

Secondary self-rated outcome measures are the Obsessive-Compulsive Inventory-Revised (OCI-R), self-rated Y-BOCS, Montgomery-Åsberg Depression Rating Scale—Self-Rated (MADRS-S), Work and Social Adjustment Scale (WSAS), Assessing Quality of Life 6 Dimensions (AQoL-6D) (for economic evaluation), Credibility/Expectancy Questionnaire (CEQ), Working Alliance Inventory—Short Form Revised (WAI-SR), the TIC-P resource use questionnaire (for economic evaluation), and the Negative Effects Questionnaire (NEQ). Participants will also rate their treatment preference measured on a 7-point Likert-type scale (pre-treatment and post-treatment).

Table 2. Assessments of secondary outcomes at different time points

	Pre-treatment	Week 4	Week 7	Week 15 (primary end-point)	7-month follow-up	16-month follow-up
Clinician-rated instruments						
SCID-5 (OCD)	X					
MINI	X					
Y-BOCS	X	X	X	X	X	X

CGI-S	X	X	X	X	X	X
CGI-I		X	X	X	X	X
PEAS*		X	X	x		
Self-rated instruments						
YBOCS-SR	X			X	X	X
OCI-R	X			X	X	X
MADRS-S	X			X	X	X
WSAS	X			X	X	X
AQoL-6D	X			X	X	X
TIC-P	X			X	X	X
NEQ				X	X	X
Other adverse events		X	X	X	X	X
CEQ**		X				
WAI-SR**		X				
Treatment preference	X			X		

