Although there are no strict guidelines regarding the selection of non-inferiority margins, half the placebo-controlled effect of gold-standard treatment is often recommended as adequate [23]. The proposed non-inferiority margin of 4 is smaller than half of the 10-point effect for ERP on the Y-BOCS [4], and would therefore be a stringent non-inferiority margin. Moreover, a non-inferiority margin of 4 points gives similar precision compared to previous non-inferiority trials for OCD in adults that have used 5 points [19] or 3 points [20], and a previous non-inferiority trial in pediatric OCD that used a margin of 4 points [30]. From a clinical point of view, a 4-point margin on the Y-BOCS is considered a small but observable difference in OCD symptoms.

Secondary outcomes

While this study was designed to have high power to assess the primary hypothesis, we do not have sufficient power to robustly compare the secondary outcomes between the treatment arms without inflating the false positive rate. This means that the results from these analyses should be interpreted with caution. On secondary outcomes, our approach will be to compute 95% confidence intervals of group differences without comparing the bounds to any predefined margin. Because the non-inferiority testing procedure will not apply, the secondary outcomes will be analyzed using an intent to treat approach including all randomized participants.

Moreover, we do not plan to collect data continuously throughout the treatments since our focus is on the pre-post comparisons. This decreases the usefulness of statistical methods that make imputations based on past observations. Therefore, unless the proportion of missing data exceeds 10%, no data imputation methods will be used as default (unless stated otherwise). However, if the proportion of missing data exceeds 10%, we will perform maximum likelihood imputations based on demographics and the scores from the pre-treatment assessment to complement the complete case analyses. The implications of these analyses on the reliability of the results will be discussed.

Time to response

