To explore whether B4DT leads to a faster treatment response than individual CBT, the proportion of responders in the two treatments will be compared 4 weeks after treatment start. The 95% confidence intervals of the odds ratio of response will be calculated for this purpose. Because the B4DT-group will have received their full treatment dose at the point of assessment while the gold standard CBT-group will have received only about 25%, there are strong reasons to believe that, from this perspective, B4DT will lead to faster symptom relief. An identical analysis will be conducted at 7 weeks to evaluate whether there is a difference between the treatments when participants in the individual CBT group have received 50% of the treatment.

Rates of response and remission

The proportion of participants in response and remission will be compared 14 weeks after treatment start. Response is defined as a reduction of 35% or more on the Y-BOCS and a CGI-I score of 1 or 2. Remission is defined as a Y-BOCS score of 12 or less and a CGI-S score of 1 or 2. Proportions will be compared using a two-sided two-proportions z-test.

Dropout rate

To explore whether the groups differ in terms of treatment completion, we will compare whether the proportion of patients that discontinue treatment prematurely differs between B4DT and gold standard CBT. A dropout will be defined as a patient in the B4DT arm that participates in less than 1.5 full days at the clinic, or a patient in the gold standard CBT arm that participates in less than 8 CBT sessions. Proportions will be compared using a two-sided two-proportions z-test.

Negative effects

To describe negative treatment effects, a two-sample t-test will be used to compare the total NEQ-scores at the primary endpoint (scores on the subscales will be presented in the supplement). The additional semi-structured questions about suicidal behaviors and thoughts, hospitalization, deterioration of psychiatric symptoms, and psychiatric care outside the study, will be reported in a frequency table.

Cost effectiveness

Health economic data will be collected using the self-rated Treatment Inventory of Costs in Psychiatric Patients (TIC-P) questionnaire [11]. The TIC-P records costs for the past month

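### The faster-response hypothesis is assessed only by responder odds ratios at weeks 4 and 7; a baseline-adjusted Y-BOCS difference should be pre-specified beside them

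*Combined protocol and SAP*

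**What the plan says.** Under Research questions, Secondary outcomes, faster response with B4DT is the only secondary hypothesis with a stated direction; the other four items say there is none. Its test is set there: "A comparison of the proportion of treatment responders at week 4 and week 7 will be used to test this hypothesis".

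Statistical analysis, Time to response, gives the method. First, "the proportion of responders in the two treatments will be compared 4 weeks after treatment start", and then "The 95% confidence intervals of the odds ratio of response will be calculated for this purpose". For the later visit, "An identical analysis will be conducted at 7 weeks to evaluate whether there is a difference between the treatments". Response is a composite: "Response is defined as a reduction of 35% or more on the Y-BOCS and a CGI-I score of 1 or 2".

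Under Measurements, the blind-rated Y-BOCS is "administered at pre-treatment, at weeks 4 and 7 during treatment", and Table 2 confirms these visits. The ANCOVA with pre-treatment score as covariate appears only under Primary outcome, for the 14-week assessment. The documents describe no continuous Y-BOCS comparison at week 4 or 7 and no repeated-measures model.

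For secondary outcomes in general, the plan will "compute 95% confidence intervals of group differences without comparing the bounds to any predefined margin", in all randomised participants, and it calls these analyses underpowered and exploratory.

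**The concern.** A yes/no response shows who crossed a threshold, not how far symptoms fell. The Time to response section itself argues that B4DT should relieve symptoms sooner, which is partly a question of amount. The score that answers it is collected blind at both visits, and a suitable model is already in the plan.

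The plan concedes low power for secondary outcomes, which is a reason to use the full score where it exists. At stake is mainly the week-7 result. By the plan's own argument a clear week-4 difference is expected. At week 7 the CBT arm has had about half its treatment, so the remaining difference could be modest. A wide odds-ratio interval might then be read as no difference in speed when the Y-BOCS means would show one.

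**Working it through.** **Inputs from the documents** (Sample size calculation): 60 per arm; 10% missing, so 60 × 0.9 = 54; baseline 22.6 (SD 3.78); CBT post-treatment 12.9 (SD 4.07).

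**Assumed, because not stated:** week-4/7 means, SD (4.07 or 5.5) and pre-post correlation ρ (0.3, 0.5 or 0.7). CGI-I is not modelled, so the figures cover only the 35% Y-BOCS rule.

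**The plan's own figure.** Non-inferiority at margin 4, true difference 0, ρ = 0: SE = 4.07 × √(2/54) = 0.783. Power = Φ(4/0.783 − 1.96) = Φ(3.15) = 99.9%. The stated >95% holds as a lower bound. No power figure is given for time to response.

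**Response rate.** Response means post ≤ 0.65 × pre, so for an arm mean m:

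p = Φ[(0.65 × 22.6 − m) / √(SD² + (0.65 × 3.78)² − 2 × 0.65 × ρ × SD × 3.78)]

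At SD 4.07 and ρ = 0.3 the denominator is √(16.565 + 6.037 − 6.000) = 4.075. As a check, m = 12.9 gives Φ(1.79/4.075) = 67%, close to the 65% response to CBT cited in the Introduction.

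**Worked case: CBT 17, B4DT 15, SD 4.07, ρ = 0.3, 54 per arm.** Power here is the chance that the 95% CI excludes no difference in B4DT's favour.

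- Response rates: Φ(−2.31/4.075) = 0.285 and Φ(−0.31/4.075) = 0.470.
- Odds ratio: log OR = 0.800; SE = √{[1/(0.285 × 0.715) + 1/(0.470 × 0.530)]/54} = 0.407; power = Φ(0.800/0.407 − 1.96) = 50%.
- ANCOVA: SE = 4.07 × √(0.91 × 2/54) = 0.747; power = Φ(2/0.747 − 1.96) = 76%.
- Per-arm n for 80% power, with (1.96 + 0.84)² ≈ 7.85: ANCOVA 2 × 7.85 × 16.565 × 0.91/4 = 59; odds ratio about 110. Loss = 1 − 59/110 = 46%.

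**Loss for a 2-point difference across assumptions**

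| Setting | n per arm, ANCOVA | n per arm, responders | Loss |
|---|---|---|---|
| Smallest: SD 5.5, ρ 0.5, 16 vs 14 (two-proportion test) | 89 | 142 | 37% |
| SD 4.07, ρ 0.3, 17 vs 15 (log OR) | 59 | 110 | 46% |
| Largest: SD 4.07, ρ 0.7, 19 vs 17 (log OR) | 33 | 101 | 67% |

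**Power at 54 per arm** (formula and simulation agree to within about two points)

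| Difference | SD | ρ | Odds ratio | ANCOVA |
|---|---|---|---|---|
| 2 points | 4.07 | 0.3-0.5 | 46-62% | 75-84% |
| 2 points | 5.5 | 0.3 | 32-33% | 49-51% |
| 3 points | 4.07 | 0.3-0.5 | 84-93% | 98-99% |
| 4 points | 4.07 | 0.3 | 98% | 99.9% |

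The narrowing depends on the SD. At SD 5.5, ρ = 0.3 and means 17 vs 13 (response 0.33 and 0.62), the odds ratio gives Φ(1.198/0.403 − 1.96) = 84% and ANCOVA gives Φ(4/1.010 − 1.96) = 98%.

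**Where the gain comes from.** Much of it is baseline adjustment. At SD 5.5, ρ = 0.7 and means 16 vs 14, an unadjusted Y-BOCS comparison needs 118.7 per arm, the responder comparison 110.0 and ANCOVA 60.5. The 35% rule already uses the baseline score, so an unadjusted mean comparison would not be a reliable improvement.

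**The case against.** **The endpoint fits the objective.** The objective is named time to response, and response is a pre-specified composite that includes CGI-I. A reader might infer that the responder comparison is the wrong main analysis and should be demoted. The documents do not support that: mean Y-BOCS answers a related but different question. This stands, and it limits the point to an added analysis.

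**The loss may not matter.** If CBT has achieved half of its 9.7-point gain by week 7 (22.6 − 4.85 = 17.75) and B4DT is at 12.9, the difference is 4.85 points and the odds ratio has 99.8-100% power at ρ 0.3-0.5. The Non-inferiority margin section calls 4 points small but observable, so 1.5 to 2.5 points may have little clinical weight. This stands as a limit on importance. Linear gain is itself an assumption, however, and the size of the week-7 difference is what the trial sets out to learn.

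**The limitation is disclosed.** The plan says secondary results are exploratory and underpowered. That lowers the stakes, but it is no reason to leave a collected, more precise measure unanalysed.

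**The scripts are elsewhere.** The plan refers to analysis code in a public repository, which is not part of these documents. A continuous analysis there cannot be ruled out; if it exists, the plan should state it.

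**Conclusion.** The point holds as a gap in pre-specification. The only directional secondary hypothesis is assessed on a dichotomised outcome, while the blind-rated score and a suitable model are both at hand.

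For a 2-point difference the loss against ANCOVA is equivalent to about 37-67% of the sample, and ANCOVA gained about 16 to 31 percentage points of power in the 2-point settings simulated. These figures rest on assumed week-4/7 means, SD and correlation, and on the Y-BOCS part of the response definition alone.

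Two stronger readings should be avoided. One is a single figure for the loss, such as roughly 45% of the sample: some plausible settings give it, but the documents do not fix it. The other is that a real early advantage would generally be missed: at SD 4.07 both analyses have near-full power from 4 points upward. The practical consequence is mainly a modest difference at week 7, in an analysis that remains exploratory.

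**What to change.** In Statistical analysis, Time to response, keep the responder odds ratios at weeks 4 and 7 as they are and add text to this effect:

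*At weeks 4 and 7, blind-rated Y-BOCS will also be compared between arms by the ANCOVA used for the primary outcome, with pre-treatment Y-BOCS as covariate, in all randomised participants and under the missing-data rule for secondary outcomes. The adjusted mean difference will be reported with its 95% CI. This analysis is exploratory.*

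If the deposited scripts already contain this, the text should say so. The model should be the baseline-adjusted one, since that is where much of the gain lies.

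Cost: two more model fits and two more exploratory intervals to report. No visits, instruments or patients are added. Stating it in advance also avoids a later choice between the two scales.

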	Written informed consent.
	To be willing and able to attend treatment at any one of the two treatment clinics, regardless of the clinic where the initial assessment took place (the two clinics are located at different locations in Stockholm, about 20 Km apart).
	Be fluent in Swedish.
Exclusion criteria	Other psychological treatment for OCD planned during trial period.
	Completed CBT with exposure and response prevention (ERP) for OCD in the last 12 months.
	Changes in psychotropic medication within the last 2 months.
	Bipolar disorder.
	Psychosis.
	Alcohol or substance dependence.
	Organic brain disorder.
	Hoarding disorder or OCD with primary hoarding symptoms.
	Suicidal ideation that would warrant close monitoring.

Abbreviations: CBT, cognitive behavior therapy; DSM-5, The Diagnostic and Statistical Manual of Mental Disorders, Fifth Edition; OCD, obsessive-compulsive disorder; Y-BOCS, Yale-Brown Obsessive-Compulsive Scale.

Randomization and concealment

A block randomization method will be applied where included participants are randomized to receive either B4DT (delivered at Ångestenheten, Psykiatri Nordväst), or gold standard CBT (delivered at OCD-programmet, Psykiatri Sydväst), regardless of their clinic of origin in blocks of 4 or 6. Block size will vary randomly. This approach was chosen to achieve balance in the allocation of participants to treatment arms and to prevent selection bias. It entails that patients assessed in one clinic may have to travel to the other clinic to receive treatment. A third party, the Karolinska Trial Alliance, will generate the randomization sequence. Participants will receive their randomization number based on order of inclusion.

Assessors will be blind to the study objectives as well as group assignment up to the last follow-up. To ensure that the blinding is maintained, assessors will be asked to guess the intervention received at each assessment after randomization, and to indicate whether the blinding has been broken (for example, the participant revealing details about the treatment). If blinding is broken, the participant will be assigned another assessor at subsequent follow-ups. The proportion of correct guesses will be estimated, and blinding is adequate if the proportion of correct guesses does not differ significantly from what would have been achieved by guessing treatment allocation by chance.

Interventions

Bergen 4-day treatment (B4DT)

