Abbreviations: AQoL-6D, Assessing Quality of Life 6 Dimensions; CEQ, Credibility/Expectancy Questionnaire; CGI-I, Clinical Global Impression–Improvement; CGI-S, Clinical Global Impression–Severity; MADRS-S; Montgomery–Åsberg Depression Rating Scale–Self-Rated; MINI, Mini International Neuropsychiatric Interview; NEQ, Negative Effects Questionnaire; OCI-R, Obsessive–Compulsive Inventory–Revised; PEAS, Patient Exposure/Response Prevention Adherence Scale; SCID-5, Structured Clinical Interview for DSM-5 Disorders; TIC-P, Treatment Inventory of Costs in Psychiatric Patients; WAI-SR, Working Alliance Inventory–Short Form Revised; WSAS, Work and Social Adjustment Scale; Y-BOCS, Yale–Brown Obsessive Compulsive Scale; Y-BOCS-SR, Yale–Brown Obsessive Compulsive Scale–Self-Rated; Other adverse events, semi-structured questions about potential severe adverse events and psychiatric care outside the study

* PEAS rated once at the last day of B4DT treatment

** CEQ and WAI-SR rated by participants at the last day of B4DT treatment and week 2 in individual CBT

Treatment-response will be defined as a $\geq 35\%$ reduction on the Y-BOCS and a Clinical Global Impression–Improvement (CGI-I) score of 1 ("very much improved") or 2 ("much improved"). Remission will be defined as a score of ≤ 12 on the Y-BOCS and a Clinical Global Impression–

Severity (CGI-S) rating of 1 ("normal, not at all ill") or 2 ("borderline mentally ill"). Recovery will be defined as a sustained remission status at the long-term follow-ups[8].

Safety and adverse events

Data on adverse events including suicidal ideation, and initiation of additional psychiatric care, will be collected at each assessment following inclusion, as well as through the regular contact between participants and therapists during treatment. A standardized self-rated questionnaire (Negative effects questionnaire, NEQ; [9]) containing 32 questions about incidents and negative effects will be used at the primary endpoint and follow-ups.

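### The adverse-event questions have no pre-treatment administration and no new-or-worsened rule, so the frequency table may mix pre-existing with new suicidal thoughts and outside care

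*Combined protocol and SAP*

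**What the plan says.** **Timing.** In Table 2 the row "Other adverse events" is marked at week 4, week 7, the primary end-point, 7 months and 16 months. The pre-treatment cell is empty. The footnote describes the row as "semi-structured questions about potential severe adverse events and psychiatric care outside the study".

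**Collection.** The section Safety and adverse events states: "Data on adverse events including suicidal ideation, and initiation of additional psychiatric care, will be collected at each assessment following inclusion".

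**Analysis.** The Negative effects section opens with the NEQ: "To describe negative treatment effects, a two-sample t-test will be used to compare the total NEQ-scores at the primary endpoint". It then turns to further items: "The additional semi-structured questions about suicidal behaviors and thoughts, hospitalization, deterioration of psychiatric symptoms", ending with "psychiatric care outside the study, will be reported in a frequency table". It gives no rule for new or worsened status, no time window and no counting unit. Secondary objective 5 also plans to compare the prevalence of severe adverse events at 14 weeks.

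**Entry.** On suicidal ideation, Table 1 excludes only "Suicidal ideation that would warrant close monitoring". On concurrent care, it excludes other psychological treatment for OCD planned during the trial. It does not exclude other ongoing psychiatric care.

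**The concern.** Two of the four tabulated items describe states that a patient can bring into the trial: suicidal thoughts and care outside the study. A patient with mild, unchanged ideation since before randomization could answer yes at every assessment. So could a patient who continues care that began before inclusion. With neither a baseline answer to the same questions nor a rule for new or worsened status, the table cannot separate such patients from those whose problem arose during the trial.

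The two wordings of the care item add to this. The safety section refers to "initiation of additional psychiatric care, will be collected at each assessment following inclusion", which is a new event. The footnote and the analysis refer to care outside the study, which can include care already under way.

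At stake is how clearly the trial describes harms. The protocol itself notes that B4DT has not been tested in a randomized trial against an active control, so readers will look at this table for any difference between the arms.

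**Working it through.** The plan states no figure on this point, so there is none to reproduce. The check has two parts.

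**1. Which items are affected**

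| Item | Nature | Can it pre-date treatment and still be reported later? |
|---|---|---|
| Suicidal behaviours and thoughts | state (thoughts) | Yes; milder ideation is allowed at entry |
| Hospitalization | dated event | No, if a date or window is recorded |
| Deterioration | change | No, by definition |
| Care outside the study | can be ongoing | Yes; most ongoing care is allowed at entry |

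**2. What mixing would do, if it occurs**

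Inputs:
- 60 patients per arm (Study Design).
- b, the share with a condition at entry that persists to the assessment, equal in both arms. Assumed range: 5 to 30%.
- p, new onset among the others. Assumed: 5% in CBT and 10% in B4DT, chosen only to give a true ratio of 2.0. The documents give neither b nor p.

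Formula: share counted, q = b + (1 − b) × p.

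Example at b = 0.20: CBT 0.20 + 0.80 × 0.05 = 0.24, or 14.4 of 60; B4DT 0.20 + 0.80 × 0.10 = 0.28, or 16.8 of 60. The ratio is 0.28 / 0.24 = 1.17. The pre-existing share of counted cases is 0.20 / 0.24 = 83% in CBT and 0.20 / 0.28 = 71% in B4DT.

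| b | Counted per 60, CBT vs B4DT | Ratio shown | Pre-existing share, CBT / B4DT | Risk difference (points) |
|---|---|---|---|---|
| 0 | 3.0 vs 6.0 | 2.00 | 0 / 0 | 5.0 |
| 5% | 5.9 vs 8.7 | 1.49 | 51% / 34% | 4.75 |
| 10% | 8.7 vs 11.4 | 1.31 | 69% / 53% | 4.5 |
| 20% | 14.4 vs 16.8 | 1.17 | 83% / 71% | 4.0 |
| 30% | 20.1 vs 22.2 | 1.10 | 90% / 81% | 3.5 |

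The dilution is on the ratio scale. The risk difference is (1 − b) × (0.10 − 0.05), which is also what new cases alone would give over all 60 patients. At b = 20%, new cases are 2.4 vs 4.8, a gap of 2.4 patients, and the counted cases 14.4 vs 16.8 have the same gap. The absolute difference is not lost, but it becomes noisier.

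**Noise.** The standard error of the arm difference is √(2q(1 − q)/60). With onset of 5% in both arms and b = 20%, counting everyone gives q = 0.24 and a standard error of 0.078. Counting new cases only gives q = 0.80 × 0.05 = 0.04 and a standard error of 0.036.

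**Chance imbalance at entry.** 1.96 × √(2b(1 − b)/60) is about ±8 points at b = 5%, ±11 at 10%, ±14 at 20% and ±16 at 30%.

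**Direction.** With equal true onset (5% in both arms) the counted shares are equal at every b and the ratio stays 1.0. Neither arm is favoured in expectation.

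**The case against.** The strongest reply is that nothing in the documents says pre-existing cases will be counted. The wording and recall window of the semi-structured questions are not given; they may ask only about events since the last contact. The analysis scripts are in a public repository outside these documents. On care, the safety section is where collection is defined, and it speaks of initiation, so the phrase in the analysis may be a shorter label for the same thing. This stands. A reader might infer that the table does count old ideation and continuing care as events, but the documents support only that it may. What remains is that the rule is unstated and the wordings differ.

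A reader might also infer that the problem cannot be repaired at analysis. That goes too far. Every candidate has a full psychiatric assessment, an exclusion criterion turns on the level of ideation, the MINI is given at pre-treatment, and the pre-treatment TIC-P covers the past month. These are not the same questions, and the plan does not assign them to this table, so the repair would be partial.

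Finally, the NEQ comparison, which opens the Negative effects section, is unaffected. Serious adverse events will be described case by case, which leaves room to state prior status. No test is specified for the frequency table, and the plan already treats secondary results as exploratory. All of this stands and limits the weight of the point.

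**Conclusion.** The point holds as a minor one. The plan collects no baseline answer to the adverse-event questions, does not restrict the frequency table to new or worsened conditions, and words the care item in two ways. For suicidal thoughts and outside care, the table may therefore overstate what arose after treatment began and understate a true ratio between arms.

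The size cannot be known from the documents. The range of about 1.5 to 1.1 for a true ratio of 2.0 rests wholly on assumed prevalence and onset, on pre-existing conditions persisting equally in both arms, and on questions that do not already ask about new events only. If they do ask only that, the ratios above do not apply.

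A reader might infer a bias that makes one treatment look safer. The documents do not support that: randomization balances pre-existing cases in expectation, and under equal true rates the expected ratio is 1.0. Nor does the point touch the primary Y-BOCS analysis.

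**What to change.** 1. **Table 2:** add the same semi-structured questions at the pre-treatment assessment. For patients already included when the change is made, name the eligibility assessment, the MINI and the pre-treatment TIC-P as the baseline source, and say that it is partial.
2. **Negative effects section:** tabulate by arm the number of patients with a new or worsened event since pre-treatment, each patient once per category, and state the time window. Show the table of all answers beside it.
3. **Care item:** reconcile the wording in Safety and adverse events with that in the Table 2 footnote and the Negative effects section, so that all three describe the same event.

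The cost is a few questions at an assessment that already includes diagnostic interviews, so a slightly longer visit, plus one revised table. The definitions can be fixed at any time before analysis. The baseline questions help only patients not yet treated; inclusion was expected to start in November 2022, so that part is best done early.
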